- 2. Clinical evidence of bowel obstruction at the time of study enrollment
- 3. Expected to use other 5HT3 antagonists or NK1 antagonists for prophylaxis during the study
- 4. Continuation of over-the-counter therapies for nausea and/or vomiting during the study
- 5. On cytotoxic chemotherapy in the high/moderate/low emetogenic risk categories or oral antineoplastic agents in the high or moderate emetogenic risk categories according to the latest NCCN guideline within 2 weeks of study enrollment
- 6. On scheduled potent CYP3A4 inducers at the time of study enrollment (avasimibe, carbamazepine, phenytoin, rifampin, efavirenz, nevirapine, barbiturates, systemic glucocorticoids, modafinil, oxcarbazine, phenobarbital, pioglitazone, rifabutin, St. John's wort, troglitazone)¹
- 7. On scheduled CYP3A4 substrates with narrow safety range at the time of study enrollment (alfentanil, cyclosporine, dihydroergotamine, ergotamine, pimozide, quinidine, sirolimus, tacrolimus)
- 8. On scheduled strong or moderate CYP3A4 inhibitors (boceprevir, clarithromycin, conivaptan, indinavir, itraconazole, ketoconazole, lopinavir/ritonavir, mibefradil, nefazodone, nelfinavir, posaconazole, ritonavir, saquinavir, telaprevir, telithromycin, voriconazole; amprenavir, aprepitant, atazanavir, ciprofloxacin, darunavir/ritonavir, diltiazem, erythromycin, fluconazole, fosamprenavir, grapefruit juice, imatinib, verapamil) within one week of study enrollment¹
- 9. Unwilling to provide informed consent
- 10. Severe renal impairment (calculated Creatinine clearance <=29 cc/min)²
- 11. Severe liver impairment (Child-Pugh Score >9)³
- 12. Females who are pregnant, lactating, or intend to become pregnant during the participation of the study; childbearing age women who are not on birth control. Positive pregnancy test for women of childbearing potential, as defined by intact uterus and ovaries, and no history of menses within the last 12 months. Pregnancy test to be performed on the day of enrollment. In cases of women with elevated b-HCG, these candidates will be eligible to participate so long as the level of b-HCG is not consistent with pregnancy and the non-pregnant status is confirmed by a Gynecologic examination.

¹ according to FDA website

http://www.fda.gov/Drugs/DevelopmentApprovalProcess/DevelopmentResources/DrugInteractionsLabelin g/ucm093664.htm

² Calculated creatinine clearance can be done within 14 days of study enrollment.

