³ T. bilirubin, albumin, prothrombin time, and serum creatinine tests can be done within 14 days of study enrollment (only if not performed in the last 14 days)

Birth Control Information

Taking part in this study can result in risks to an unborn or breastfeeding baby. Patients should not become pregnant, breastfeed a baby, or father a child while on this study. Sexually active patients must use birth control during the study.

Birth Control Specifications: Women who are able to become pregnant must use birth control during the study and for 30 days after the last NEPA dose.

Acceptable forms of birth control for men and women include barrier methods (such as condom or diaphragm) with spermicide, or abstinence.

Males must tell the doctor right away if their partner becomes pregnant or suspects pregnancy.

Pregnant women will not be enrolled on this study. If the patient becomes pregnant or suspects that she is pregnant, she must inform her doctor right away. Pregnancy may result in removal from this study.

D.3. Study screening. A 2 step consent process will be used. First, a verbal consent will be obtained by the study staff to proceed with screening of potential participants for eligibility and to characterize their nausea and vomiting. Outpatients may be contacted by phone within 1 week prior to their scheduled clinic visit to inform them of this study so they can make necessary arrangements if interested in participating. Eligible patients will then be formally enrolled onto the study after they have signed the informed consent indicating a willingness to participate in the trial. The number of patients screened, approached, eligible, and enrolled will be documented. Reasons for refusal for eligible patients will also be captured.

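### Exclusion 12 defines women of childbearing potential the wrong way round, which could mislead staff about whom to test for pregnancy

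*Combined protocol and SAP*

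**What the plan says.** Exclusion 12 (section D.2, Table 2) has several parts:

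- It excludes "Females who are pregnant, lactating, or intend to become pregnant during the participation of the study".
- It excludes women of childbearing age who are not using contraception. That age range is not defined.
- It makes a positive pregnancy test an exclusion for "women of childbearing potential, as defined by intact uterus and ovaries, and no history of menses within the last 12 months".
- It fixes the timing of the test: "Pregnancy test to be performed on the day of enrollment". The sentence does not say who is tested.
- It deals with raised b-HCG from other causes: "In cases of women with elevated b-HCG, these candidates will be eligible to participate so long as" two conditions are met, namely that "the level of b-HCG is not consistent with pregnancy and the non-pregnant status is confirmed by a Gynecologic examination".

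The Birth Control Information that follows Table 2 states that taking part can carry risks to an unborn or breastfed child. It adds "Pregnant women will not be enrolled on this study" and "Sexually active patients must use birth control during the study". It also says "Women who are able to become pregnant must use birth control during the study and for 30 days after the last NEPA dose". A patient who suspects pregnancy must tell her doctor at once.

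Table 4 (after section D.12) lists a pregnancy test among the screening procedures and does not limit it to any group of women. Section E lists suspected pregnancy among the reasons for discontinuing a patient.

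**The concern.** A definition of childbearing potential should pick out women who could conceive. With uterus and ovaries intact, recent menstruation is evidence that a woman can conceive, and a year without it is the usual description of a postmenopausal woman. Exclusion 12 requires the absence of menses, so it describes roughly the opposite of the intended group.

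This is an operative eligibility rule and not background text. If staff use it to decide who needs a test, a woman with regular periods could be enrolled untested, and a pregnancy she does not know about could be missed. The protocol itself recognises the risk to an unborn child. By section D.7, a patient randomized to NEPA who continues into the extension would take it on days 6, 11, 16 and 21.

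**Working it through.** No arithmetic applies. The plan states no figure on this point, and the documents do not give the expected number of women, their ages or their menstrual status. The check is to apply the definition as written, look for other text that corrects it, and see what the remaining safeguards do.

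**Step 1. Apply the definition literally.** It has two conditions, both required: intact uterus and ovaries, and no menses in the past 12 months.

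- A woman with intact organs who has menstruated within the year fails the second condition. She is not of childbearing potential under the text, so the positive-test exclusion does not reach her.
- A woman with intact organs and no menses for a year meets both conditions. She is of childbearing potential under the text and is covered.
- A woman without uterus or ovaries fails the first condition and is not covered, as intended.

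The first two groups are the wrong way round.

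**Step 2. Look for a competing definition.** There is none. Exclusion 12 also speaks of childbearing age, and the Birth Control Information speaks of women able to become pregnant, but neither gives criteria. The second expression does show what the plan has in mind, and the definition in exclusion 12 does not match it.

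**Step 3. Ask who is tested.** Two places call for the test: the timing sentence in exclusion 12 ("Pregnancy test to be performed on the day of enrollment") and the screening row of Table 4. Neither names a group. Grammatically, the definition qualifies the positive result that excludes a woman; it does not qualify the instruction to test. Staff may therefore test every woman, or they may look for a criterion and find only the inverted one. The text permits both.

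**Step 4. See what the other safeguards do.**

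| Safeguard | Where | When it acts |
|---|---|---|
| Bar on pregnant women | Exclusion 12, first clause; Birth Control Information | Once pregnancy is known |
| Raised b-HCG must be explained | Exclusion 12, last sentence | Once b-HCG has been measured |
| Exclusion for lack of contraception | Exclusion 12 | Before entry; lowers the chance of pregnancy |
| Contraception during the study | Birth Control Information | After entry |
| Duty to report suspected pregnancy; discontinuation | Birth Control Information; section E | After entry, if pregnancy is suspected |

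None of these depends on the faulty definition, so all still operate. None of them says which women are to be tested at entry. Table 4 shows the pregnancy test at enrollment only, so no later scheduled test would find a pregnancy missed at that point.

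**The case against.** The strongest reply is that the slip changes little. The definition is attached to the result that excludes a woman and not to the order to test. Table 4 restricts testing to nobody, so a site that follows the schedule could test all women. A woman whose test is positive because she is pregnant is barred by the first clause of exclusion 12 and by the Birth Control Information, whatever her menstrual history. Women of childbearing age without contraception are already out, which lowers the chance of an unrecognised pregnancy among those with recent menses. Staff would probably see that the phrase is reversed. Harm would require them to apply it literally and the woman to be pregnant without knowing it.

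Most of this stands, and it limits the point in two ways. A reader might infer that the protocol lets a pregnant woman enroll if she has menstruated recently. It does not: "Pregnant women will not be enrolled on this study" carries no such qualification. A reader might also infer that the protocol directs staff to test the wrong women. That too goes beyond the text, because neither test instruction refers to the definition. What the documents support is that the definition could mislead.

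What remains is that the only stated criterion for the group says the opposite of what is meant. The other bars act once a pregnancy is known or b-HCG has been measured, and the contraception rules do not detect an existing pregnancy. An eligibility rule should not depend on staff noticing that it is wrong.

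A further fair objection concerns the remedy. Simply removing the negative would take every woman with intact organs and a year without menses out of the definition. In a cancer population, absence of periods need not mean inability to conceive. That is general clinical reasoning and not protocol text, but it is a reason to write the correction with more care.

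**Conclusion.** Wrong as written; minor. Exclusion 12 contains a drafting error that reverses its only definition of women of childbearing potential, so that the positive-test exclusion literally omits women with recent menses and covers women with none for 12 months. That much follows from the wording alone.

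The practical consequence rests on an assumption: that some staff would use this definition to decide whom to test, since nothing else in the document tells them. If every woman is tested, the error has no effect on detection. The separate bars, the contraception requirements and the discontinuation rule keep the risk small even if the definition is used. The number of women concerned cannot be estimated from the documents. The error does not touch the target of 30 evaluable patients, the power statement or any analysis in section H.

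**What to change.** Replace the definition in exclusion 12 with one that agrees with the Birth Control Information, which refers to women able to become pregnant. An example is a woman with intact uterus and ovaries who has had at least one menstrual period in the preceding 12 months. The sponsor should decide, as a clinical matter, how to treat women with intact organs whose absence of periods need not mean infertility, and write that decision into the definition. The same amendment should state that women meeting the definition are tested at enrollment, so that the test instruction no longer leaves the group open.

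The cost is a wording amendment and possibly some additional pregnancy tests, the number depending on how sites now read the rule. Sample size, randomization and analysis do not change.

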IND Agent: NEPA (300mg Netupitant/0.5mg Palonosetron) Capsule (Refer to Investigator's Brochure for further information)

Chemical Name: 2-[3,5-Bis(trifluoromethyl)phenyl]-N-[6-(4-methylpiperazin-1-yl)-4-o-tolylpyridin-3-yl]-N-methylisobutyramide

Mode of Action: NEPA is a fixed combination of netupitant, a substance P/neurokinin 1 (NK) receptor antagonist, and palonosetron, a serotonin-3 (5-HT) receptor antagonist

Description: NEPA (300mg netupitant/0.5mg palonosetron) capsules are hard gelatin capsules with white body and caramel cap with "HE1" printed on the body. Placebo for NEPA will be identical hard gelatin capsules with the "HE1" imprinted on the body.

How Supplied: Helsinn will supply NEPA and Placebo capsules to the site. The capsules are packaged as 1 capsule per blister pack/box.

Note: NEPA/Placebo may be repackaged from the supplied bottles and dispensed in pharmacy dispensing bottles according to the quantities specified by the investigator.

Storage: The recommended long term storage condition for NEPA/placebo capsules is USP controlled room temperature. Store at 20-25 °C (68-77 °F). Excursions permitted to 15-30 °C (59-86 °F).

Stability: NEPA/Placebo has a shelf-life of 4 years from date of manufacture.

Route(s) of Administration: Oral

Method of Administration: It is recommended patients should take NEPA (300mg netupitant/0.5mg palonosetron)/Placebo (1 capsule) orally with or without food.

Please refer to the NEPA package insert for safety profile and side effects/drug interactions.

Potential Drug Interactions: CYP3A4 Interactions:

 Akynzeo should be used with caution in patients receiving concomitant medications that are primarily metabolized through CYP3A4. The plasma concentrations of CYP3A4 substrates can increase when co-administered with Akynzeo. The inhibitory effect on CYP3A4 can last for multiple days. Patients on these medications will be monitored while on study.

Concomitant and Prohibited Medication

- Concomitant medications must be recorded in the electronic medical record from 28 days prior to the first dose of study drug through the last dose of study drug.
- The use of rescue medications will be allowed (metoclopramide 10 mg q4h PRN for breakthrough nausea).

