D.4. Randomization. To be eligible for the blinded phase, individuals will need to have an average nausea NRS \geq 4/10 prior to randomization on a day between day 3 and day 7 (i.e. day 5 +/-2). Patients who report a significant clinical response to placebo (i.e. NRS <4/10) during this time on the placebo run-in would not proceed to the double-blind phase and will be monitored until day 7 in case their nausea level increased again, in which case they will be eligible to proceed and will be randomized. Participants without significant clinical response to placebo will be randomized to either NEPA or placebo through Clinical the Trial Conduct website https://biostatistics.mdanderson.org/ClinicalTrialConduct/DeskTopDefault.aspx) in a 2:1 ratio, and stratified by level of nausea NRS (average over past 24 hours, 4-6 vs 7-10) obtained prior to randomization.

D.5. Blinding. During placebo run-in, only the patient will be blinded and told that he/she will receive one of the two study treatments (Akynzeo or placebo). During the randomized phase, both the patient and the research staff conducting the assessment will be blinded to the treatment assignment. NEPA and identically appearing placebo will be dispensed by Dispensing Pharmacy at MD Anderson; only the pharmacy team will be aware of the identity of this study agent. Allocation concealment will be

maintained. We will check the blinding from patients and study staff at the end of study (Table 4).

Unblinding Procedures:

1. The Statistician and the investigational pharmacist will have access to the codes/assignments.

2. The codes will be revealed with prior approval from the DSMB and IRB only if there is a safety issue and the treating physician needs to be aware of the treatment assignment.

3. The PI should be contacted regarding and give approval for un-blinding

4. The Investigator/research team must inform the IND Office when un-blinding occurs.

D.6. Research staff. An orientation will be held with research staff involved in this study to introduce them with the study design and to standardize the provision of each intervention.

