F. Investigator Communications with Helsinn

As stipulated in 2.6 of the Strategic [name] Anderson is the sponsor and assumes all obligations regarding the preparation and submission of individual and aggregate safety reports to FDA, Ethic Committee, and other relevant persons to the extent required by and as per the applicable US laws, regulations, and guidelines. The Principal Investigator will forward to Helsinn any serious adverse reaction (i.e. for which it is judged there is a reasonable causal relationship between the study drug and the adverse event) on the MedWatch Form, regardless of its expectedness, within 24 hours from first awareness, including follow-ups.

The Principal Investigator shall provide Helsinn with relevant safety data including study and IND safety reports (prior to their finalization) and any safety signal or risk (with the rationale) originating from the study. The e-mail address for exchanging all the above mentioned safety information is: [contact].

Attribution	Grade 1	Grade 2	Grade 3	Grade 4	Grade 5
Unrelated	Phase I	Phase I	Phase I	Phase I	Phase I
			Phase II	Phase II	Phase II
				Phase III	Phase III
Unlikely	Phase I	Phase I	Phase I	Phase I	Phase I
-			Phase II	Phase II	Phase II
				Phase III	Phase III
Possible	Phase I	Phase I	Phase I	Phase I	Phase I
	Phase II	Phase II	Phase II	Phase II	Phase II
		Phase III	Phase III	Phase III	Phase III
Probable	Phase I	Phase I	Phase I	Phase I	Phase I

Recommended Adverse Event Recording Guidelines

					Page 17 of 22
	Phase II	Phase II	Phase II	Phase II	Phase II
		Phase III	Phase III	Phase III	Phase III
Definitive	Phase I	Phase I	Phase I	Phase I	Phase I
	Phase II	Phase II	Phase II	Phase II	Phase II
		Phase III	Phase III	Phase III	Phase III

Adverse events will be captured according to the recommended AE recording guidelines for a Phase II protocol.

G. Serious Adverse Event Reporting

An adverse event or suspected adverse reaction is considered "serious" if, in the view of either the investigator or the sponsor, it results in any of the following outcomes:

- Death
- A life-threatening adverse drug experience any adverse experience that places the
 patient, in the view of the initial reporter, at immediate risk of death from the adverse
 experience as it occurred. It does not include an adverse experience that, had it
 occurred in a more severe form, might have caused death.
- Inpatient hospitalization or prolongation of existing hospitalization

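### The unblinding rule in D.5 requires prior DSMB and IRB approval for every safety code break, and the protocol states no urgent route

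*Combined protocol and SAP*

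**What the plan says.** Section D.5 has a short list under "Unblinding Procedures". Its four items do the following.

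- Item 1 names who holds the codes: "The Statistician and the investigational pharmacist will have access to the codes/assignments".
- Item 2 sets the approvals and the first condition: "The codes will be revealed with prior approval from the DSMB and IRB only if there is a safety issue". It adds a second condition, that the physician treating the patient must have a need to know the arm.
- Item 3 adds the PI: "The PI should be contacted regarding and give approval for un-blinding".
- Item 4 is a notification: "The Investigator/research team must inform the IND Office when un-blinding occurs".

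The list gives no time limit for the approvals, no out-of-hours contact and no provision for approval or notification after the event.

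**The concern.** The single ground on which the protocol permits unblinding is also the ground on which time may matter. Item 2 pairs a safety issue with a treating physician's need to know. It then puts two bodies ahead of the release, neither of which is described as available at short notice. The people who hold the codes are given no authority to release one without those approvals.

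At stake is the care of an individual patient. Allocation is 2:1, so about one third of randomised patients receive no NEPA during the blinded phase, and a physician who simply assumes active drug would be wrong for them. The protocol gives one reason why the assignment might bear on urgent care. Section C says of CYP3A4 that "The inhibitory effect on CYP3A4 can last for multiple days", so a recent capsule may still matter when another drug is needed.

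**Working it through.** There is no figure in the plan to reproduce. The check is a reading of D.5 against the rest of the protocol, with one small calculation on how far interrupting the drug helps.

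**1. Steps named in D.5**

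| Party | Role | Timing stated |
|---|---|---|
| DSMB | approves (item 2) | prior |
| IRB | approves (item 2) | prior |
| PI | should be contacted and approve (item 3) | none stated |
| IND Office | informed (item 4) | when unblinding occurs |
| Statistician, investigational pharmacist | hold the codes (item 1) | no release authority stated |

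Two approvals are expressly prior. The PI's approval would naturally come first too, but the text does not say so.

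**2. Search for another route**

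- D.9 (stopping rules) covers placebo responders, withdrawal and replacement of dropouts.
- D.12 names the PI, IRB and DSMB as monitors and describes no rapid decision process.
- Section E covers withdrawal and adverse event classification.
- Section F sets a clock for sending serious adverse reactions to the drug supplier: "regardless of its expectedness, within 24 hours from first awareness, including follow-ups". This is a reporting deadline and does not open the code.
- Section G asks for a written report to the IND Office within 24 hours (next working day) for unexpected, related, life-threatening or fatal events. This too is reporting only.
- Section H sends periodic response and toxicity summaries to the IND Office Medical Monitor.
- Section I refers to a protocol-specific monitoring plan but does not cite it for unblinding.

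None of these states a second way to break the code. The protocol therefore expects urgent events and sets clocks for reporting them, but sets none for telling the physician what the patient took.

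**3. Who is affected**

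- In the run-in everyone takes placebo and only the patient is blinded (D.1, D.5), so staff already know the treatment.
- Patients whose nausea score stays below 4 through day 7 are not randomised (D.4).
- The extension is open label (D.1).
- The rule therefore bites on randomised patients in the blinded phase, with capsules on days 6 and 11 (D.7).

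Section H gives 30 evaluable patients and accrual of 41-50. It does not give the number randomised.

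**4. Does interrupting the drug make the code unnecessary?**

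B.4 gives netupitant a half-life of 80 +/- 29 hours. Assuming simple first-order decay, the fraction left after t hours is 0.5^(t/half-life).

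- 24 hours: 0.5^(24/80) = 0.81.
- 5 days: 0.5^(120/80) = 0.35.
- 5 days, half-life 80 - 29 = 51 hours: 0.5^(120/51) = 0.20.
- 5 days, half-life 80 + 29 = 109 hours: 0.5^(120/109) = 0.47.

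Interrupting further capsules needs no code, but it does not quickly remove one already taken.

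**The case against.** The best defence is that the need will seldom arise. Scheduled narrow-safety-range CYP3A4 substrates, strong or moderate inhibitors and potent inducers are exclusions (D.2, Table 2). Section C repeats the inhibitor and substrate restrictions and addresses a new need for such drugs during the trial. It also says that patients on CYP3A4-metabolised medicines will be monitored, and it lets the investigator delay or interrupt dosing for an adverse event. Section E lets a patient be discontinued for an adverse event. Neither step needs the code. D.7 reports low rates of drug-related effects in an earlier repeated-cycle trial (constipation 3.6%, headache 1%). All of this stands, and it limits the weight of the point. It does not remove the case in which an emergency calls for a new drug after a capsule has been taken.

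A second defence is that an institutional policy or the monitoring plan may already supply an emergency route. That is possible. The claim is therefore only that the protocol states none and that its unblinding procedures cite none.

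A reader might also infer several stronger things that the documents do not support:

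- That all 41-50 patients are exposed to the rule. That figure is total accrual and includes people who are never randomised.
- That three prior approvals are mandatory. The word is attached only to the DSMB and IRB, and the PI item says should.
- That the pharmacist could release a code within minutes. No turnaround time or out-of-hours cover is given.
- That these patients take many other medicines. A medication history is collected, but no such figure is reported.
- That the rule will provoke off-protocol code breaks. Nothing in the documents bears on this.

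**Conclusion.** The point holds on the text of D.5. This is a stated rule, not a missing detail: followed literally, an urgent code break for a randomised patient in the blinded phase waits for the DSMB and the IRB, with the PI's approval also expected. The conclusion assumes that no document outside the protocol overrides D.5.

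Neither the length of the delay nor the number of patients who would meet it can be derived from the documents; the safeguards in Section C and Table 2 suggest that cases would be few. The matter is one of trial conduct and patient safety. It leaves the estimate of change in nausea, the power statement and the planned analyses as they are. It should be corrected because the remedy is cheap, not because frequent harm has been shown.

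**What to change.** Split item 2 of the unblinding procedures in D.5, and align item 3 with it.

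- **Urgent.** When a patient's urgent care depends on the assignment, the investigational pharmacist releases that one patient's code to the treating physician without prior approval. The break is documented, and the PI, IND Office, DSMB and IRB are notified afterwards.
- **Non-urgent.** All other requests keep prior DSMB and IRB approval and the PI's approval, as now.

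The text should also say how the pharmacist is reached out of hours, since D.5 does not. If an institutional emergency procedure already exists, citing it in D.5 would serve the same purpose.

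The cost is a few lines of protocol wording and a slightly higher chance that one patient is unblinded unnecessarily. Confining the release to a single code and to the treating physician keeps that cost small. No dose, treatment rule, sample size or analysis changes.
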